# Statistical Analysis Plan

Taisho Pharmaceutical R&D Inc.  
Protocol TS121-US201

Statistical Analysis Plan (SAP)

Final 2.0  
18 Dec 2018  
CONFIDENTIAL

## Serious Adverse Event

AEs that result in death, life-threatening, requiring inpatient hospitalization or prolongation of existing hospitalization, persistent or significant disability/incapacity, a congenital anomaly or birth defect, or any other important medical event, as defined in the CSP Section 11.2.1, will be recorded as serious adverse events (SAE).

## Event of Clinical Significance

AEs that are suicidal ideation and behavior or lens opacity, as defined in the CSP Section 11.3, will be recorded as events of clinical significance (EOCS).

### **6.1.3.2 Clinical Laboratory Tests**

Laboratory tests listed in the CSP Section 9.2.7.8 will be performed at times indicated in Schedule of Procedures, Table 1.

### **6.1.3.3 Vital Signs**

Vital signs will include systolic and diastolic blood pressure (mmHg), pulse rate (bpm) and oral temperature (°C) and will be collected at specified time points indicated in the Schedule of Procedures, Table 1.

### **6.1.3.4 Electrocardiograms**

Electrocardiograms will be assessed for

- Ventricular rate (beats per minute [bpm])
- RR interval (msec)
- PR interval (msec)
- QRS duration (msec)
- QT interval (msec)
- QT interval corrected using the Bazett correction formula (QTcB) (msec)
- QT interval corrected using the Fridericia correction formula (QTcF) (msec)

The ECG will be evaluated by the Investigator as 'Normal', 'Abnormal, NCS' or 'Abnormal, CS'. Any abnormal CS ECG will be reported as an AE.

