4.4.3 Known and Potential Risks to Human Subjects

Though the relevance to human subjects is not yet fully understood, nonclinical findings suggested that potential risks include cataract, hepatotoxicity, effects on the gastrointestinal system and effects on the renal system. To date, no apparent trends related to these potential risks were noted in the clinical studies.

Treatment emergent ventricular arrhythmias have been reported following single and multiple dose administrations of TS-121. During the SAD study (TS121-US101), two subjects exposed to 2.5 mg of TS-121 had defined intervals of ventricular arrhythmias while on telemetry. Plasma levels were approximately 50% of C_{max} values (40 to 70 ng/mL). The events were without symptoms, resolved without intervention, and produced no residual effects. The events were considered mild in intensity and possibly related to the study drug. One subject was discontinued from the trial, and one subject completed the trial.

In the MAD study (TS121-US102), one subject showed a single episode of 4 consecutive premature ventricular contractions without symptoms while on telemetry approximately 15 hours

after receiving 50 mg dose of TS-121 on Day 9. The investigator assessed the episode as a clinically significant event and described the event as mild and possibly related to TS-121. The subject completed the trial with no additional events.

In a PET receptor occupancy study (TS121-US103), no abnormal ECG results were reported following single TS-121 doses of up to 50 mg. See Sections 8 and 9 of the Investigator's Brochure for additional information.

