 13. Patients who are undergoing treatment with drugs that might influence HPA axis function, including psychotropic medications, benzodiazepines, metyrapone, lithium and/or corticosteroids
[Please refer to Section 8.3 for a more detailed list of prohibited concomitant medications]
 14. Patients who need/plan to take moderate to strong CYP3A4 inhibitors/inducers (food, beverages, medications and supplements) during this study (see Appendix 1)
 15. Patients who work night shifts or need to work night shifts during the trial
 16. Females who are pregnant, intend to become pregnant (within 90 days of the last dose), or who are breastfeeding
 17. Patients with significant hepatic, renal, cardiovascular, hemodynamic, pulmonary, gastrointestinal, hematological, locomotor, immunologic, ophthalmologic, metabolic, neurological, or endocrine disease that in the opinion of the investigator would confound participation or study results

18. Patients with clinically significant ECG* findings at Visit 1 or Visit 3, or hematology, biochemistry, or urinalysis abnormalities at Visit 1 (abnormal laboratory values considered to be not clinically significant as per the investigator are acceptable)
[* Note: QTcF interval of > 450 msec in males or > 470 msec in females, will be the basis for exclusion from the study; ECG may be repeated once for confirmatory purposes, if an initial value is obtained that exceeds the values specified]
19. Patients with history or presence of cataract (lens opacities with vision disturbances), glaucoma, chronic inflammatory eye disease, significant eye trauma, any ophthalmic surgical procedure (e.g. cataract or glaucoma) or any ocular laser surgery in either eye
20. Patients with lens opacity based on ophthalmological examination performed at Visit 2 as listed below:
- Nuclear opalescence (NO) with a LOCSIII classification > 3.0 in either eye
 - Nuclear color (NC) with a LOCSIII classification > 3.5 in either eye
 - Cortical lens opacities (C) with a LOCSIII classification > 2.0 in either eye
 - Posterior subcapsular lens opacities (P) with a LOCSIII classification > 0.3 in either eye
21. Patients with a history (within 5 years) or presence of malignancy at Visit 1
[Note: History (within 5 years) of non-metastatic, non-progressive basal and/or squamous cell carcinoma of the skin, in situ cervical and prostate cancer are exceptions (currently in remission)]

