10.5.1.4 Electrocardiogram

Characteristics of cardiac events at each reading and changes from baseline will be summarized descriptively for interval data (ventricular rate, RR, PR, QRS and QTc) will be calculated for each group. The incidence of abnormalities, based on the clinical interpretations from the investigator, will be enumerated.

QTc as corrected by the Fridericia and Bazett methods will be used as the primary measure of change in QT interval. Changes from baseline for each of the ECG parameters will be summarized using descriptive statistics. Borderline and prolonged QTc will be listed and

frequency table provided. Additionally, the numbers of patients with change from baseline in QTc at appropriate visits categorized as <30 msec, 30 to 60 msec, and >60 msec, will be tabulated and summarized by treatment group as will the number of patients with a QTc interval >500 msec.

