## **6.3.16.1 Adverse Events**

The following AE listings will be produced:

- All AEs [Listing 16.2.7.1]
- SAEs [Listing 16.2.7.2]
- AEs leading to Study Drug Discontinuation [Listing 16.2.7.3]
- EOCSs [Listing 16.2.7.4]
- Overdose [Listing 16.2.7.5]

The following information will be included in AE listings: Subject number, age, sex and race, treatment group, verbatim term, MedDRA preferred term (PT), system organ class (SOC), SAE indicator flag, AE onset date (and time) and study day, AE end date (and time), duration (days), severity, relationship to study drug, action taken for study drug, action taken to treat, AE outcome, and treatment emergent (TEAE) flag. Adverse events with onset date on or later than date of first dose of the randomized treatment, which also meet one of the following two criteria, will be considered TEAE.

- The AE was not present prior to the first dose of study drug for the treatment period
- The AE was present prior to the first dose of study drug for the treatment period and increased in severity

Each summary tabulation of AEs will include the number and percentage of patients who experienced TEAEs grouped to treatment (TS-121 10 mg, TS-121 50 mg and placebo) and the number and percentage of all patients who experienced AEs during placebo lead-in.

The overview of AEs includes the number and percentage of patients with at least one AE, with any SAE or with an AE that led to study discontinuation [Table 14.3.1.1].

Tables of number (and percentage) of patients with AEs summarized by SOC, PT and maximum severity [Table 14.3.1.2] and by SOC, PT and relationship to investigational product [Table 14.3.1.3] will be presented by treatment group for the safety analysis population. Treatment related AEs include those that are marked as “possibly”, “probably” or “definitely related to

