### **6.3.16.4 12-Lead Electrocardiogram**

Electrocardiogram data (ventricular rate, RR, PR, QT, QTcB and QTcF interval data, QRS duration) will be listed [Listing 16.2.9.2.1] with the Investigator interpretation. Any QTcF or QTcB  $>500$  msec will be flagged in the listing. Electrocardiogram data change from baseline will be listed [Listing 16.2.9.2.2] and each flagged to distinguish QTc change from baseline 30 to 60 msec or  $>60$  msec.

Descriptive summaries (n, mean, SD, SE, CV%, minimum, median and maximum) of interval data observed values and change from baseline will be presented by treatment and time point [Table 14.3.6.2.1 and Table 14.3.6.2.2]. Baseline is defined as the scheduled predose assessment of Visit 3. Only if scheduled Visit 3 result is missing, will the latest predose assessment be used as the baseline for that subject number and test.

The categorical analysis of QTcB and QTcF will be presented in a frequency table of patients categorized based on maximum post-baseline QTc ( $\leq 500$  msec or  $>500$  msec) and maximum change from baseline ( $<30$  msec, 30 to 60 msec, and  $>60$  msec) [Table 14.3.6.2.3].

The incidence of abnormalities, based on the clinical interpretations from the Investigator, will be enumerated by treatment group and visit [Table 14.3.6.2.4].

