## **SECTION 14.3.6: Other Safety Assessments**

Table 14.3.6.1.1	Vital Signs Observed Values (Safety Analysis Population)
Table 14.3.6.1.2	Vital Signs Change from Baseline (Safety Analysis Population)
Table 14.3.6.2.1	Quantitative 12-Lead Electrocardiogram Assessments, Observed Values (Safety Analysis Population)
Table 14.3.6.2.2	Quantitative 12-Lead Electrocardiogram Assessments, Change from Baseline (Safety Analysis Population)
Table 14.3.6.2.3	Categorical Summary of 12-Lead Electrocardiogram QTc (Safety Analysis Population)
Table 14.3.6.2.4	Summary of 12-Lead ECG Interpretations (Safety Analysis Population)
Table 14.3.6.3.1	Body Weight Observed Values (Safety Analysis Population)
Table 14.3.6.3.2	Body Weight Change from Baseline (Safety Analysis Population)
Table 14.3.6.4.1	Ophthalmological Examination Class I Lens Events (Safety Analysis Population)
Table 14.3.6.4.2	Ophthalmological Examination LOCS III Grading and Best Corrected Visual Acuity Score Observed Values (Safety Analysis Population)
Table 14.3.6.4.3	Ophthalmological Examination LOCS III Grading and Best Corrected Visual Acuity Score Change from Baseline (Safety Analysis Population)
Table 14.3.6.5.1	Columbia Suicide Severity Rating Scale (C-SSRS) Shift from Baseline (Safety Analysis Population)
Table 14.3.6.5.2	Columbia Suicide Severity Rating Scale (C-SSRS) Suicidal Ideation Score Observed and Change from Baseline (Safety Analysis Population)

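### The ECG interpretation table counts abnormal readings visit by visit, so it shows prevalence rather than incidence and gives no by-arm count of patients who become newly abnormal but not clinically significant

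*SAP*

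**What the plan says.** SAP 6.1.3.4 sets three levels of investigator reading: "The ECG will be evaluated by the Investigator as 'Normal', 'Abnormal, NCS' or 'Abnormal, CS". The next sentence gives the top level a second route into the report: "Any abnormal CS ECG will be reported as an AE".

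The tabulation is in SAP 6.3.16.4: "The incidence of abnormalities, based on the clinical interpretations from the Investigator, will be enumerated by treatment group and visit [Table 14.3.6.2.4". Protocol 10.5.1.4 promises the same quantity without saying how baseline is handled: "The incidence of abnormalities, based on the clinical interpretations from the investigator, will be enumerated". The SAP's list of tables has one output for these readings, "Summary of 12-Lead ECG Interpretations (Safety Analysis Population". It lists no shift table and no worst-category table for them.

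Four other provisions bear on the point.

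- **Entry.** Exclusion 18 (Protocol 7.1.2) removes "Patients with clinically significant ECG* findings at Visit 1 or Visit 3", with QTcF limits in a note. An NCS abnormality at Visit 3 is not a bar to randomization.
- **Repeats.** SAP 6.3.1 allows one assessment per patient per time point in summary tables. After the first treatment-period dose it takes the first of any repeated values. The rule that lets an unscheduled assessment fill a missing visit (SAP 6.3.4) is written for clinical laboratory data only.
- **Adverse events.** Treatment emergence is judged against the period before randomized dosing. One qualifying condition in SAP 6.3.16.1 is "The AE was not present prior to the first dose of study drug for the treatment period"; the other is an increase in severity.
- **Listing.** Every reading appears by patient with its interpretation in Listing 16.2.9.2.1.

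**The concern.** Incidence means new cases among patients who did not have the condition at the start. A count of abnormal tracings at Week 2, Week 4 and Week 6 is something else. A patient who is Abnormal NCS at Visit 3 and stays so is counted at every visit. A patient who becomes abnormal is cancelled in the count by one who normalises. A new abnormality seen at a single visit adds one to a single column, and one seen only on a repeat tracing may not reach the table at all.

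Safety and tolerability against placebo is a primary objective (Protocol 5.1), and the cardiac background is stated in Protocol 4.4.3: "Treatment emergent ventricular arrhythmias have been reported following single and multiple dose administrations of TS-121". A reader of the report would want to know how many patients with a normal Visit 3 tracing became abnormal on 10 mg, on 50 mg and on placebo. For changes judged NCS, no planned table answers that.

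The same SAP does better elsewhere. QTc is classified per patient by maximum post-baseline value and maximum change (6.3.16.4). Laboratory results get baseline-to-end-of-treatment shift tables, and laboratory outliers are counted over scheduled and unscheduled tests (6.3.16.2). Two C-SSRS items get a shift from Visit 3 (6.3.16.7).

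**Working it through.** **What the by-visit counts can and cannot give.** The plan states no figure to reproduce. Take 60 patients in an arm (Protocol synopsis), with 12 abnormal at Visit 3 and 12 at Week 6. If the same 12 are abnormal both times, there are 0 new cases. If all 12 normalise and 12 others become abnormal, there are 12. The two by-visit counts are identical across the whole range from 0 to 12, so the number newly abnormal cannot be recovered from them.

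**Size of the dilution.** The documents give no ECG abnormality rate, so every rate below is an assumption.

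- n = 60 per arm; share Abnormal NCS at Visit 3, b = 0.25; 90% of these still abnormal at a later visit.
- New abnormality among patients normal at Visit 3: 2% on placebo, 10% on 50 mg.
- f = 1 if a new finding persists; f = 0.25 if it shows at only one of the four post-baseline visits (Visits 4 to 7).

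By-visit proportion = 0.9b + (1 − b) × new × f. The comparison measure is the difference divided by its standard error (SE), with SE = √[(p₁(1 − p₁) + p₂(1 − p₂))/n].

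- **By visit, persistent.** Placebo 0.225 + 0.75 × 0.02 = 24.0%; 50 mg 0.225 + 0.75 × 0.10 = 30.0%. SE = √[(0.1824 + 0.2100)/60] = 0.081. Ratio 0.06/0.081 = 0.74.
- **By visit, transient.** 0.225 + 0.75 × 0.005 = 22.9%; 0.225 + 0.75 × 0.025 = 24.4%. Ratio 0.015/0.0775 = 0.19.
- **Shift, persistent.** Patients normal at Visit 3: 60 × 0.75 = 45 per arm; 2% vs 10%. SE = √[(0.0196 + 0.0900)/45] = 0.049. Ratio 0.08/0.049 = 1.62.
- **Shift through Visit 6, transient.** Only three of the four visits count, so 1.5% vs 7.5%. SE = √[(0.0148 + 0.0694)/45] = 0.043. Ratio 0.06/0.043 = 1.39.

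Results as b varies:

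| b | By visit, persistent | By visit, transient | Shift, persistent | Shift to Visit 6, transient |
|---|---|---|---|---|
| 15% | 0.96 | 0.26 | 1.73 | 1.48 |
| 25% | 0.74 | 0.19 | 1.62 | 1.39 |
| 40% | 0.54 | 0.14 | 1.45 | 1.24 |

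**Stress test: background on placebo.** If 10% of the 25% normalise (2.5 points) and placebo prevalence is to stay at 25%, then 2.5/75 = 3.3% of the baseline-normal patients must read abnormal at each visit. Over three visits that is between 3.3% (the same patients) and 10% (different patients each time). Take 10% in both arms and keep the 8-point drug excess.

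- **Persistent.** Shift 10% vs 18%: 0.08/√[(0.0900 + 0.1476)/45] = 1.10. By visit 25% vs 31%: 0.06/√[(0.1875 + 0.2139)/60] = 0.73.
- **Transient.** Shift 10% vs 16% (three quarters of the excess): 0.06/√[(0.0900 + 0.1344)/45] = 0.85. By visit 25% vs 26.5%: 0.015/√[(0.1875 + 0.1948)/60] = 0.19.

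The advantage shrinks but keeps its direction.

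**Second set of assumptions.** Let baseline NCS abnormality persist at b = 20%, with transient new abnormality at each visit of q = 2% on placebo and 8% on active among the rest. By visit, b + (1 − b)q gives 21.6% vs 26.4%. Any new abnormality over Visits 4 to 6, 1 − (1 − q)³, gives 5.9% vs 22.1% among 48 patients per arm. A 16-point difference per patient appears as about 5 points per visit.

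**The case against.** The strongest reply is that little of clinical weight is lost. A new CS reading is an adverse event, is coded to a preferred term, and is counted once per patient by arm under a rule that refers to baseline. CS findings are excluded at entry, so such an event should be new. QTc already has a per-patient worst-case table. The Phase 1 arrhythmias were seen on telemetry, and the one in the multiple-dose study was judged clinically significant; an event so judged here would be tabulated as an adverse event. All of this stands.

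A reader might infer that new abnormalities on TS-121 are hidden. The documents do not support that: the CS ones are tabulated and the rest are listed by patient. A reader might also infer that this table is the only planned output able to show a rhythm or morphology change. It is not. The coded adverse-event tables can name a rhythm disorder, while Normal, Abnormal NCS and Abnormal CS name none. The proposed shift table could not separate ventricular ectopy from any other abnormality either.

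Pre-existing NCS findings should balance between arms on average, so they blur the comparison without favouring an arm. The table shells are a separate document that is not available here. SAP 6.3.1 places Visit 3 in the treatment period, so the table may well carry a baseline row. Such a row would show baseline prevalence by arm but would still not cross-classify patients.

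The adverse-event route does not close the gap entirely. It depends on the CS or NCS judgment made at about 25 sites, and a change judged NCS enters no table that refers to baseline. The documents do not show that the arrhythmia signal would fall in that category.

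**Conclusion.** The point holds in a narrow form. Table 14.3.6.2.4 gives prevalence at each visit under the name of incidence. No planned output summarises by arm the patients who go from Normal to Abnormal NCS, or each patient's worst category, and repeat post-dose tracings are left out of summary tables. The consequence is dilution of the comparison with placebo, without directional bias and without loss of the CS events.

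That the by-visit counts cannot recover new cases follows from the table's design and needs no assumption. The size does: at 25% abnormal at baseline the ratio is about 0.2 to 0.7 by visit and about 1.4 to 1.6 for the shift. With a 10% background of new readings in both arms, the shift falls to about 0.9 to 1.1. None of these ratios reaches 1.96, so the shift table would describe the data better but would not by itself settle a difference of this size. This is a cheap improvement in a trial that both documents call a pilot.

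**What to change.** In SAP 6.3.16.4:

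1. Keep the by-visit counts in Table 14.3.6.2.4, but call them prevalence of abnormal readings at each visit.
2. Add a by-arm shift table. Rows: the Visit 3 interpretation (Normal, Abnormal NCS, Abnormal CS), under the baseline rule already in that section. Columns: each patient's worst post-baseline interpretation over scheduled, repeat and unscheduled ECGs through Visit 6 or early termination. Show follow-up separately.
3. Report the number newly abnormal over the number normal at Visit 3, by arm, among randomized and treated patients with a post-baseline ECG. The denominator must be stated, because the safety population also includes patients who took only lead-in placebo.
4. State that the one-value-per-visit rule in SAP 6.3.1 does not apply to this table.

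The cost is one more table from data already listed, with no further ECGs. A worst-reading summary is more sensitive to a single odd tracing and raises the background rate in every arm, so it should be read beside the by-visit counts and the adverse-event tables.

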# Statistical Analysis Plan

Taisho Pharmaceutical R&D Inc.  
Protocol TS121-US201

Statistical Analysis Plan (SAP)

Final 2.0  
18 Dec 2018  
CONFIDENTIAL

## **6.1.3.5 Weight**

Body weight will be recorded in kilograms (kg) at specified time points indicated in the Schedule of Procedures, Table 1.

## **6.1.3.6 Physical and Neurological Examination**

Physical and neurological examinations will be performed and recorded as described in the Schedule of Procedures, Table 1.

The results will be recorded in the patient's study source records. Any abnormalities noted prior to first administration of the investigational product will be listed as medical history. Findings after first administration of the investigational product that meet the criteria of an AE (CSP Section 11.1) will be captured as AEs.

## **6.1.3.7 Ophthalmological Examination**

Ophthalmological examinations will include the following:

- Best corrected visual acuity as measured with the ETDRS chart, and scored in LogMAR
- Evaluation of the crystalline lens through a maximally dilated pupil using lens opacities classification system (LOCS III), including the following features;
  - Posterior subcapsular cataract (P)
  - Cortical cataract (C)
  - Nuclear opalescence (NO)
  - Nuclear color (NC)

Events of clinical significance (EOCS) for ophthalmological findings, as defined in CSP Section 11.3.2, will be recorded as AEs.

## **6.1.3.8 Columbia Suicidal Severity Rating Scale (C-SSRS)**

C-SSRS (Screening, Version 1/14/09) which pertains to the previous 6 months will be administered at Visit 1, and then C-SSRS (Since Last Visit, Version 1/14/09) which pertains to changes since the last visit will be administered at Visits 3 through 7.

At a minimum, responses to questions 1 (Wish to be Dead), 2 (Non-Specific Active Suicidal Thoughts) and suicidal behaviors will be recorded.

# Statistical Analysis Plan

Taisho Pharmaceutical R&D Inc.  
Protocol TS121-US201

Statistical Analysis Plan (SAP)

Final 2.0  
18 Dec 2018  
CONFIDENTIAL

The suicidal ideation score is calculated as the maximum score of responses to the first 5 questions.

- Wish to be dead (positive response is scored 1)
- Non-specific active suicidal thoughts (positive response is scored 2)
- Active suicidal ideation with any methods (not plan) without intent to act (positive response is scored 3)
- Active suicidal ideation with some intent to act, without specific plan (positive response is scored 4)
- Active suicidal ideation with specific plan and intent (positive response is scored 5)

The suicidal ideation score will be set Not Applicable (numeric score = 0) when Item 1 and Item 2 responses are negative. An EOCS for suicidal ideation and behavior, as defined in CSP Section 11.3.1, may be recorded for any patient who has a C-SSRS suicidal ideation score of 5 or a “yes” response for any of the C-SSRS suicidal behavior questions.

The suicidal ideation intensity rating will be calculated as the sum of numbers endorsed on 5 intensity items (Frequency, Duration, Controllability, Deterrents and Reasons for Ideation).

